#### **10.4.3 Analysis of the Secondary Endpoints**

Efficacy: A DFS curve will be created using the Kaplan-Meier method based on all patients considered to be evaluable based on having received protocol treatment, provided that adequate patients are enrolled in order to address this following an amendment to increase accrual.

The response to treatment will be determined for patients who receive treatment; the response rate for those patients who are evaluable for response, along with a 95% two-sided confidence interval will be reported.

As another secondary endpoint, all the evaluable patients will have determinations of many immune parameters at baseline, 3 months, and 6 months. The changes in the parameters obtained from blood samples will be determined at baseline vs. 3 months, and baseline vs. 6 months. The changes in the parameters obtained from biopsies will be obtained from baseline vs. a single second biopsy at 6 months. As an illustration, we will assume that a total of 25 paired tests will be considered of equal, primary importance. Paired results from 24 evaluable patients, including those used in the initial run-in portion who are treated at the highest safe dose, will be formed and tested for a difference from zero using a two-sided 0.002 significance level paired t-test, to

allow an overall 0.05 significance level test, applying a very conservative Bonferroni adjustment to the set of approximately 25 paired comparisons. In practice, comparisons of the paired values will likely be performed using a Wilcoxon signed rank test instead of a paired t-test, and a Hochberg adjustment may be used instead of an overly stringent Bonferroni adjustment.

Another secondary objective is to evaluate the pharmacokinetic parameters of Vicineum obtained by urine samples. This will be a descriptive analysis and will report sample statistics such as mean, standard error, median, minimum, maximum and other descriptive measures only.

Urinary EpCAM will be measured and will be compared between patients who have a clinical response to therapy vs. those who do not respond. The results will be presented for both response categories using descriptive statistics such as mean, standard error, median, minimum, maximum and other descriptive measures. Although it is expected to have low power, a comparison of the EpCAM levels may be compared between the two response categories using a Wilcoxon rank sum test, with the resulting p-value intended to help describe the differences noted.

PD-L1 and PD-1 levels will be obtained at baseline and after treatment with both agents. The change in levels will be determined between the two measurements, and these changes will be compared between responders and non-responders, as well as between those who respond or have SD (clinical benefit=CR+PR+SD) and those with PD. Although it is expected to have low power, in each case the comparisons between the two response categories will be made using a Wilcoxon rank sum test, with the resulting p-value intended to help describe the differences noted.

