#### 1.1.2 Secondary Objectives

- To assess potential predictive biomarkers and biomarkers of the immune response in bladder tissue, urine, and peripheral blood to durvalumab and Vicineum when administered in combination to subjects with BCG-refractory high-grade NMIBC
- To assess the pharmacokinetics of Vicineum with urine samples
- To assess if urinary EpCAM correlates with response to therapy
- To assess the preliminary antitumor activity of durvalumab and Vicineum when administered in combination to subjects with BCG-refractory high-grade NMIBC
- Assess PD-L1 expression and PD-1 expressing T cells in paired bladder biopsies pre and post treatment with durvalumab and Vicineum as a marker of response/benefit

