**The following fields of data should be collected from PD-L1 testing laboratory:**

- Are the negative and positive controls stained correctly
- Is the H&E material acceptable
- Is morphology acceptable
- Total percent positivity of PD-L1 in tumor cells
- PD-L1 status (positive, negative or NA) in tumor cells
- Total percent positivity of PD-L1 in infiltrating immune cells

The Ventana SP263 assay to measure PD-L1 in tumors is experimental. As with all tests, there is a chance of false positive (the test shows high PD-L1 when it is not there) or false negative (the test does not show PD-L1 when it is there) results may occur.

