### Quality control of samples to be used for PD-L1 testing

- Tissue should be assessed by the site pathologist prior to PD-L1 testing.
- Each sample should be reviewed for:
  - Adequate fixation
  - Good preservation of morphology
  - Presence of tumor tissue

- Histopathology consistent with indication
- Greater than 100 tumor cells are required to determine PD-L1 status – tumor cell content must be reviewed prior to testing in order for PD-L1 obtain a valid result.

If indicated, shipping samples to a PD-L1 testing laboratory

- When submitting sample to for PD-L1 testing the recommendation is to ship the block in order for sectioning to occur at the laboratory. Blocks should be shipped - containing enough material to be provided to allow a minimum of 5, and preferably 10, sections to be cut (each 4 micron thick) to be used for PD-L1 testing.

Sectioning instructions

- Where it is not possible or indicated to ship the block to laboratory for PD-L1 testing, unstained slides should be prepared from the paraffin-embedded tumor sample block as described below:
  - A minimum of 5-10 x 4 micron ( $\mu\text{m}$ ) thick, unstained sections should be provided for PD-L1 testing
  - A new disposable microtome blade must be used for each block to prevent contamination between Slides are stable under these conditions for 6 months.
  - patient samples
  - Apply one section per slide to positively-charged Superfrost glass slides
  - The sections should be dried overnight between room temperature and 37°C. Do not dry sections at temperatures above 37°C.

Sections should be stored at ambient temperature and protected from light until use or shipment to testing lab by courier at ambient temperature. It is recommended that slides are cut freshly prior to PD-L1 testing and they are used within 90 days of being cut to obtain PD-L1 status

Any additional FFPE tissue obtained that is not used for PD-L1 testing can be used for the following additional correlative assays:

1. Tissue Immune Correlates - (FFPE or frozen tissue specimens) - pre-treated and post-treated samples can be analyzed by IHC (FFPE) for Epcam, TILs, CD4, CD8, Tregs, MDSCs, Macrophages, and monocytes. In addition, mesenchymal markers such as vimentin, TWIST, Snail, Slug, and Sip1 may also be assayed by IHC.
2. Frozen tissue specimens or a single FFPE slide can be analyzed later for tumor mutational load through targeted sequencing panel.

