#### **6.2.3 Response Criteria**

Patients will be evaluated every 3 months as per standard of care with cystoscopy. Biopsy will be done at PI discretion pending cystoscopic findings. Any biopsies done will be for clinical reasons to rule out tumor recurrence, however, extra biopsy material if available will be used for research purposes.

Evaluable for toxicity: All patients will be evaluable for toxicity from the time of their first treatment with vicineum or durvalumab. All observed toxicities will be tabulated using CTCAE v5.0.

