##### **6.2.4.2 Complete Response Rate for CIS**

In patients with any component of CIS upon study entry, the complete response (CR) rate will be determined at 3 months, 6 months, and 12 months from the start of Vicineum therapy. Complete response will be defined as the absence of CIS upon follow-up biopsies. These rates can be compared to historical rates of CR for CIS at these various time points.

**Abbreviated Title:** Durvalumab & Vicineum for NMIBC

**Version Date:** 05/22/2025

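### Tumour-cell PD-L1 change by response is selected by the outcome itself, and the CR+PR+SD versus PD split cannot be formed from the protocol's definitions

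*Combined protocol and SAP*

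**What the plan says.** The secondary objective in Section 1.1.2 reads, in part, "Assess PD-L1 expression and PD-1 expressing T cells in paired bladder biopsies pre and post treatment with durvalumab and Vicineum". The stated purpose is to see whether these measures indicate who responds or benefits. Section 10.4.3 turns this into two comparisons of change: "these changes will be compared between responders and non-responders, as well as between those who respond or have SD (clinical benefit=CR+PR+SD") versus those with PD. Both use a Wilcoxon rank-sum test with a descriptive p-value.

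Four other parts of the protocol bear on whether that change exists and how the groups are formed.

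- Quality control for PD-L1 testing (Section 5.1.3.2.3): "Greater than 100 tumor cells are required to determine PD-L1 status". Presence of tumour tissue is also on the checklist.
- Section 6.2.4.2, for patients with a CIS component: "Complete response will be defined as the absence of CIS upon follow-up biopsies".
- Section 6.2.3, on follow-up tissue: "Biopsy will be done at PI discretion pending cystoscopic findings".
- The second sample is the last biopsy on trial in the Study Calendar (3.4) and the sample schedule (5.2), but a single biopsy at 6 months in Sections 10.2 and 10.4.3.

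The PD-L1 laboratory also records "Total percent positivity of PD-L1 in infiltrating immune cells", separately from the tumour-cell score.

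**The concern.** The response that defines the groups also decides whether the tumour-cell measurement can be made. A CIS patient in complete response at the second biopsy has no CIS to score. A patient with a clean cystoscopy may have no biopsy. The missing values therefore fall mostly in one group, and no rule says how a tumour-free biopsy is handled.

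The clinical-benefit split has a separate fault: the protocol does not define the classes it uses.

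What is at stake is a named secondary objective. Followed as written, the plan would compare non-responders with a small, atypical set of responders, or would compare tumour-free mucosa with baseline tumour. Either result could be misread as a treatment effect on PD-L1.

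**Working it through.** **Can the groups be formed?** Section 6.2.4 says response is classified by the definitions that follow it. Those definitions are:

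| Section | What is defined |
|---|---|
| 6.2.4.1 | Recurrence-free survival; low-grade papillary tumour is not recurrence |
| 6.2.4.2 | CR, only with a CIS component, at 3, 6 and 12 months |
| 6.2.4.3 | Progression as upstaging, and PFS |
| 6.2.4.4 | Time to recurrence |

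PR and SD do not appear. Papillary-only Ta/T1 disease is eligible (2.1.1.1) but has no response class. High-grade recurrence at the same stage is not upstaging, so it is neither CR nor PD. The CR+PR+SD versus PD split cannot be assigned from this text. The responder split can be assigned only for patients with CIS, and no single time point is named.

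**Which responders can be scored?**

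- Tumour-free at the second biopsy: no tumour-cell score, under the 100-cell rule.
- No second biopsy: no score.
- Responded, then relapsed, with the last biopsy used: tumour may be present.
- Low-grade papillary tumour, which does not count as recurrence: tumour may be present.

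The last two rows are the scorable responders. They are failed or atypical ones.

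**The plan's own power figure.** Section 10.2 states 90% power for 24 pairs, effect size 1.0 SD of the change, two-sided alpha 0.05/25 = 0.002. For a paired t-test, df = n − 1 and noncentrality = 1.0 × √n. With n = 24, df = 23 and noncentrality 4.90, power is 90.2%, so the figure reproduces. The responder comparison has no N, effect size or power of its own.

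**Size of the problem.** Section 1.2.3 reports 5/12 responders at 12 weeks (41.7%). Applied to 24 patients this gives 24 × 5/12 = 10 responders and 14 non-responders. Let m responders be scorable against 14 scorable non-responders. The smallest attainable exact two-sided rank-sum p is 2/C(m+14, m). Power is simulated (4,000 runs, exact test, two-sided 0.05) for an assumed 1 SD shift.

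| m | Smallest p | Power |
|---|---|---|
| 0 | not computable | – |
| 1 | 2/15 = 0.133 | 0% |
| 2 | 2/120 = 0.017 | about 16% |
| 3 | 2/680 = 0.003 | about 28% |
| 5 | 2/11,628 = 0.0002 | about 40% |
| 10 | about 0.000001 | about 60% |

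If tumour-cell PD-L1 is one of the 25 paired tests, the same loss affects the within-patient analysis. With 14 + 5 = 19 pairs, power is 75%. With the 14 non-responders only, noncentrality is √14 = 3.74 and power is 49%.

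Fourteen scorable non-responders is itself an upper figure. Under the 6-month reading, a patient stopped at 3 months for high-grade recurrence (3.6.1) has no later biopsy scheduled; the post-treatment visits in Section 3.6 are history, examination and laboratory tests.

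**Baseline alternative.** For 10 versus 14, a two-sample t-test at two-sided 0.05 has noncentrality d/√(1/10 + 1/14). Power is 79% at d = 1.2 and 82% at d = 1.25. This is the sensitivity of the added analysis, not the size of the fault, and it assumes all 24 baseline samples are scorable.

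**The case against.** The strongest defence is that the comparison can still be run, and much of it stands. CR means absence of CIS, not absence of all tumour. With the last biopsy on trial as the second sample, a relapsing responder can supply tumour. Section 1.2.3 says about half of the early responders were sustained beyond 12 months, so perhaps 5 of 10 could be scorable, and 5 versus 14 is computable. The endpoint also covers PD-1-expressing T cells and immune-cell PD-L1, which might be read in tumour-free bladder, and the 100-cell minimum is stated for PD-L1 testing only.

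A reader might infer that the responder arm must be empty, that most responders will have no biopsy, or that none of the response classes is defined. The documents do not support any of these. Zero scorable responders is one end of a range. Biopsies are listed every 3 months as indicated and are named in the 21- and 24-month evaluations, which is not reconciled with Section 6.2.3. CR for CIS and progression are defined.

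None of this removes the selection. Responders who become scorable by relapsing do not represent response. Immune-cell readings in mucosa, set against baseline tumour, mix treatment effect with tissue type, and the plan does not say that such tissue would be scored.

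The plan also discloses a limit: "Although it is expected to have low power, in each case the comparisons between the two response categories will be made using a Wilcoxon rank"-sum test. That addresses precision, not missingness caused by the outcome or groups that are undefined.

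**Conclusion.** The point holds in a limited form. Tumour-cell PD-L1 change is not scorable in responders who are tumour-free at the second biopsy or have no biopsy, and those who can be scored are mainly relapsed or low-grade cases. The between-group comparison of that measure is selected by outcome. The clinical-benefit comparison cannot be formed as written. PD-1+ T-cell and immune-cell PD-L1 change may be measurable, but a contrast of tumour-free mucosa with baseline tumour is confounded by tissue type.

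The size depends on how many responders are scorable, which the documents do not give: from no comparison at all to about 40% power with 5. This rests on 24 patients, the 5/12 rate, 14 scorable non-responders and a 1 SD shift, all of which are assumptions for this comparison. The exact 95% interval for 5/12 runs from 15% to 72%, so the 10/14 split is itself uncertain.

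The analysis is secondary and descriptive. The primary safety conclusion is not affected.

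**What to change.** In Section 10.4.3:

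1. Replace both response splits by one: free of high-grade disease versus not, at the 3-month evaluation. This applies to CIS and papillary disease alike and needs no PR or SD.
2. Add a comparison of baseline tumour-cell PD-L1, immune-cell PD-L1 and PD-1 between these groups. It sits beside the pre/post objective and does not replace it.
3. Report tumour-cell PD-L1 change descriptively, only in patients with scorable tumour at both times. Give the number scorable in each response group and make no between-group test.
4. Report immune-cell PD-L1 and PD-1+ T-cell change separately, stating whether the follow-up tissue was tumour or tumour-free.
5. Reconcile the second-biopsy time, which is 6 months in Sections 10.2 and 10.4.3 and last biopsy on trial in Sections 3.4 and 5.2.

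The cost is wording: no new samples, and scores that are already planned. The test of tumour-cell PD-L1 change as a marker of response is given up. The added baseline comparison would detect only large differences, about 1.2 SD.

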#### **10.4.4 Safety Analyses**

All patients will be evaluated for the grades of toxicity identified, and the number of patients will DLTs at each dose level will be reported. The MTD will be identified based on being the dose level at which 0 or 1 patient in 6 has a DLT. All toxicities will be tabulated.

#### **10.4.5 Baseline Descriptive Statistics**

Demographic and clinical characteristics of all patients will be reported.

#### **10.4.6 Planned Interim Analyses**

None will be performed.

#### **10.4.7 Subgroup Analyses**

None will be performed.

#### **10.4.8 Tabulation of Individual Participant Data**

None will be provided.

### **11 COLLABORATIVE AGREEMENTS**

#### **11.1 COOPERATIVE RESEARCH AND DEVELOPMENT AGREEMENT (CRADA)**

This Protocol will be carried out under a collaboration between NCI, Sesen Biotherapeutics Inc. and AstraZeneca AB. Sesen Biotherapeutics will provide Vicineum (VB4-845) under NCI CRADA #3149, and AstraZeneca will provide Durvalumab (MEDI 4736) under NCI CRADA #3155.

## **12 HUMAN SUBJECTS PROTECTIONS**

### **12.1 RATIONALE FOR SUBJECT SELECTION**

Subjects from all racial/ethnic groups and both sexes are eligible for this study if they meet the eligibility criteria.

### **12.2 PARTICIPATION OF CHILDREN**

Individuals under the age of 18 will not be eligible for participation in this study based on the fact that patients under 18 are unlikely to have this disease and there are unknown toxicities in pediatric patients.

### **12.3 PARTICIPATION OF SUBJECTS UNABLE TO GIVE CONSENT**

Adults unable to give consent are excluded from enrolling in the protocol. However, re-consent may be necessary and there is a possibility, though unlikely, that subjects could become decisionally impaired. For this reason and because there is a prospect of direct benefit from research participation (section [12.4](#)), all subjects  $\geq$  age 18 will be offered the opportunity to fill in their wishes for research and care, and assign a substitute decision maker on the “NIH Advance Directive for Health Care and Medical Research Participation” form so that another person can make decisions about their medical care in the event that they become incapacitated or cognitively impaired during the course of the study.

Note: The PI or AI will contact the NIH Ability to Consent Assessment Team (ACAT) for evaluation to assess ongoing capacity of the subject and to identify an LAR.

Please see section [12.5.1](#) for the consent procedure.

### **12.4 EVALUATION OF BENEFITS AND RISKS/DISCOMFORTS**

Patients may benefit from the study as treatment may delay or avoid having the bladder removed. All care will be taken to minimize side effects, but they can be unpredictable in nature and severity. Patients will be examined and evaluated prior to enrollment. All evaluations to monitor the treatment of patients will be recorded in the patient chart. If patients suffer any physical injury as a result of the participation in this study, immediate medical treatment is available at the Clinical Center, National Cancer Institute, Bethesda, Maryland.

Although no compensation is available, any injury will be evaluated and treated in keeping with the benefits or care to which patients are entitled under applicable regulations. In all publications and presentations resulting from this trial, patients’ anonymity will be protected to the maximum extent possible. Authorized personnel from the National Cancer Institute (NCI) and Food and Drug Administration (FDA) or other regulatory authorities may have access to research files in order to verify that patients’ rights have been safeguarded. In addition, patient names will be given to the Central Registration to register and verify patients’ eligibility.

#### **12.4.1 Study Agents Risks**

Potential adverse reactions attributable to the administration of the study agents utilized in this trial are discussed in sections [14.1.2](#) and [14.2.2](#). Additional information is located in the investigator brochures.

#### **12.4.2 Research Blood Sampling Risks**

Side effects of blood draws include pain and bruising, lightheadedness, and rarely, fainting.

#### **12.4.3 Risks from Bladder Procedures**

Risks associated with cystoscopy, TURBT, biopsies and catheterization include: burning when passing urine, blood-tinged urine, bladder infection or the need to urinate frequently following the procedures. The insertion of a catheter into the bladder through the urethra may cause discomfort. There is also a small risk that these procedures, particularly cystoscopy, TURBT and biopsies, could damage the lining of the bladder or cause a perforation of the bladder. This could lead to urine or drugs leaking out of the bladder causing severe side effects.

#### **12.4.4 Non-Physical Risks of Genetic Research**

- Risk of receiving unwanted information: Anxiety and stress may arise as a result of the anticipation of unwanted information regarding disease. Subjects will be clearly informed that the data related to genetic analysis is coded, investigational and will not be shared with family members or health care providers. However, as specified above in Section [5.4.3](#), subjects who have indicated a desire to be informed of these data will be given an opportunity.
- Risk related to possibility that information may be released: This includes the risk that data related to genotype or risk for disease tendency or trait can be released to members of the public, insurers, employers, or law enforcement agencies.
- Risk to family or relatives: Family members or relatives may or may not want to be aware of familial tendencies or genetic risks of disease which may cause anxiety about possible future health problems.

#### **12.4.5 Radiation Risks**

The risk of radiation exposure is expected from up to 1 CT scan a year. The total estimated effective dose for one year is approximately 1.4 rem.

#### **12.4.6 CT Contrast Risks**

Itching, hives or headaches are possible risks associated with contrast agents that may be used during CT imaging. Symptoms of a more serious allergic reaction include shortness of breath and swelling of the throat or other parts of the body. Very rarely, the contrast agents used in CT can cause kidney problems for certain patients, such as those with impaired kidney function.

#### **12.4.7 Electrocardiogram Risks**

Other than possibly experiencing some minor skin irritation from the electrodes, there are no anticipated risks related to complete the electrocardiogram and/or the echocardiogram.

### **12.5 CONSENT PROCESS AND DOCUMENTATION**

The informed consent document will be provided as a physical or electronic document to the participant or consent designee(s) (e.g. legally authorized representative [LAR] if participant is an adult unable to consent) for review prior to consenting. A designated study investigator will carefully explain the procedures and tests involved in this study, and the associated risks, discomforts and benefits. In order to minimize potential coercion, as much time as is needed to

review the document will be given, including an opportunity to discuss it with friends, family members and/or other advisors, and to ask questions of any designated study investigator. A signed informed consent document will be obtained prior to entry onto the study.

The initial consent process as well as re-consent, when required, may take place in person or remotely (e.g., via telephone or other NIH approved remote platforms used in compliance with policy, including HRPP Policy 303) per discretion of the designated study investigator and with the agreement of the participant/consent designee(s). Whether in person or remote, the privacy of the subject will be maintained. Consenting investigators (and participant/consent designee, when in person) will be located in a private area (e.g., clinic consult room). When consent is conducted remotely, the participant/consent designee will be informed of the private nature of the discussion and will be encouraged to relocate to a more private setting if needed.

Consent will be documented with required signatures on the physical document (which includes the printout of an electronic document sent to participant) or on the electronic document.

Signatures on electronic documents are described below. Note: FDA only regulates electronic signatures (i.e., an electronic timestamp is generated at the time of signature) in FDA regulated research.

Manual (non-electronic) signature on electronic document:

When a manual signature on an electronic document is used for the documentation of consent at the NIH Clinical Center, this study will use the following to obtain the required signatures:

- Adobe platform (which is not 21 CFR Part 11 compliant); or,
- iMedConsent platform (which is 21 CFR Part 11 compliant)

During the consent process, participants and investigators will view individual copies of the approved consent document on screens at their respective locations (if remote consent); the same screen may be used when in the same location but is not required.

Both the investigator and the participant will sign the document using a finger, stylus or mouse.

Note: Refer to the CCR SOP PM-2, Obtaining and Documenting the Informed Consent Process for additional information (e.g., verification of participant identity when obtaining consent remotely) found [https://nih.sharepoint.com/sites/NCI-CCR-OCD-Communications/SitePages/OEC-Administrative---Clinical-Research-\(ADCR\).aspx?Mode=Edit](https://nih.sharepoint.com/sites/NCI-CCR-OCD-Communications/SitePages/OEC-Administrative---Clinical-Research-(ADCR).aspx?Mode=Edit).

